Beneficial Effects of Quinoa (*Chenopodium Quinoa* Willd) in the Prevention of Type 2 Diabetes Mellitus

version 1.

August 2020 for ClinicalTrials.org

Study protocol

This study was a pilot clinical trial according to a cross-over design developed in IDIBAPS-Hospital Clinic de Barcelona.

Participants

Subjects included, from whom informed consent was obtained for experimentation and study was performed in accordance with The Code of Ethics of the World Medical Association, were males and females ≥ 65 years old with glucose levels between 100 and 125 mg/dL and without a previous diagnosis of diabetes. Participants were excluded from the study if they did not consume a diet with daily presence of grains or cereals derivatives, tubers or/and legumes, or they presented any other health problem that the research staff considered contraindicated.

Nine subjects were included and all participants provided written informed consent, and the study protocol was approved by the Ethics Committee of Hospital Clinic de Barcelona.

Measures

- Anthropometrics: Subjects were weighed and measured without clothing and shoes. BMI was calculated as weight (kg)/height (m)², and waist circumference was measured at the midpoint between the last rib and the iliac crest and hip circumference at the widest point of the gluteus.
- Blood pressure was taken after individuals sat quietly for 5 min in a clinical examination room. The mean of three different measurements, obtained every 3 min using an OMRON M6 AC sphygmomanometer, was recorded.
- Fasting blood samples were collected by a nurse and they were analyzed by the Biomedical Diagnosis Centre (CDB) in Hospital Clinic de Barcelona.

- Nutritional patterns were measured using a 14-days dietary record revised corrected by a nutritionist and analyzed by the validated DIAL nutritional calculation program.
- Glucose fluctuations were measured by FreeStyle Libre® Flash Glucose Monitoring System (Abbott Laboratories) which measures interstitial fluid glucose concentrations. The sensor was applied by researchers on to the back of the upper arm of subjects using the applicator and participants were trained to obtain electronically all the glucose records concentrations every 15 minutes so they had to scan at least once every eight hours.

Study design

The study was a cross-over pilot clinical study consisting of two periods. The first period was only an observational and monitoring phase where participants just continued with their regular diet (RD), for this reason all participants initiated this period and wash-out term was no needed. Subsequently, with the data of the first phase obtained, the subjects began the second period in which they had to undergo a nutritional intervention with a quinoa diet (QD).

[figure not shown]
A total of six visits plus two quinoa products collection days were programmed (**Figure 1**). After the pre-study visit (V0) which took place a week before start nutritional intervention and where researchers obtained signed informed consent, participants were summoned for a first visit (V1) where they were explained how they should fill in the dietary records and they were applied with the FreeStyle Libre®.

Subjects then began RD, a period of 4 weeks during which only their normal life was monitored. After the first 14 days of this, a second visit (V2) was made where the dietary record was collected that would serve to account for their usual consumption of cereals, flours, tubers and legumes, the FreeStyle Libre® sensor was also collected.

The last day on RD period, on day 28, they were cited (V3) in consultation where blood samples after an 8 hours fast, anthropometrics measurements and blood pressure measure where obtained and for the placement of the new FreeStyle Libre® sensor. Participants were asked about their physical activity and exercise practice during those past 4 weeks by a short questionnaire adapted from the Minnesota Leisure Time Physical Activity Questionnaire for individuals of advanced age (VREM questionnaire) and a new empty 14-day dietary record was given. In addition, the volunteers received the first foods with quinoa to initiate QD the next day. Products were delivered weekly, for conservation reasons but also to ensure that they followed an adequate consumption, they had to go through consultation to pick up the product and gave the researchers the empty packs where quinoa products had been.

On the next visit the day 42 (V4) the Freestyle Libre® sensor was collected and the filled dietary record was collected. Finally, after 28 days of quinoa diet they were summoned for the last visit the day 56 (V5) where all the determinations were repeated identically as V3.

Figure 1. Study design and visits

Study food

With the premise that the products created replaced not only grains, legumes or tubers, but also farinaceous commonly consumed by the participants and that only the cereal fraction was modified, similar products based on quinoa flour were created. The creation of these products was necessary, after conducting a market search where it was observed that there was not enough food to replace those consumed since these had percentages of quinoa flour not exceeding 20-30%.

Thus, apart from delivering quinoa, quinoa flakes and quinoa flour to the participants, they were given products created with $\geq 70\%$ quinoa flour and were biscuits, crackers, brioche, sponge cake, baguette bread, sliced bread and pasta (**Table 1**). Moreover, a quinoa-based recipe was delivered with eight commonly consumed recipes that replaced the tuber, legume or grain of the recipe. Each subject received the equivalent of what they

consumed according to their RD dietary records. Thus, only if the volunteer had indicated that he consumed sponge cake was the quinoa-based product delivered to him.

Table 1. Comparison of nutritional values of products marketed in a regular diet with similar ingredients than products based on quinoa for the study.

[figure not shown]
Statistical analyses

Calculations and Statistical Analyses

Descriptive data are presented as the mean and standard deviation (SD) or median and interquartile range (IQR) for continuous variables, and the frequencies and percentages (%) for categorical variables. Anthropometric measurements, blood test variables and dietary intake were compared at different times using the non-parametric Wilcoxon signed rank test because normality and equality of variance could not be assumed due to small sample size (n=9). In order to compare variables related to dietary patterns, mean value for dietary intake, including all meals, was considered for each participant.

The glucose level monitoring sensor takes measurements at discrete time points for each patient (**Figure 2 A**). Therefore, firstly the glucose curves have been linearly interpolated in order to have observations for each patient at equal time points (**Figure 2 B**). A first sight to the glucose curves over the day shown that they were more homogeneous around breakfast than around other later meals intakes. Therefore, the glucose concentration values corresponding to the breakfast were considered as a function of time in minutes over the interval $t = [-30, 120]$, that begins half an hour before the start of breakfast and ends two hours later. Before constructing a functional model, the functional data were time aligned in order to reduce the differences between different patients and/or different days (for instance, some patients could mark the starting time of breakfast systematically before than others, or spend systematically more time in breakfast than the average) (**Figure 2 C**). The time alignment has been done by warping functions, using the function WFDA in the R package fdapace.

Figure 2. Glucose concentrations of patients (A) at discrete time points (B) at equal time points with interpolation (C) as aligned curves

Once the glucose level curves have been synchronized, a functional regression analysis was conducted to model the effect of diet type, patient and nutrient intake on monitored glucose levels. Three different explanatory variables have been considered: diet type with two categories (regular and Quinoa diets), patient indicator (categorical variable with nine levels) and the contents in different nutrients. The breakfast glucose curves are handled as the functional response variable. To study the relationship between these variables function on scalar regression (fosr) models were used.

Firstly, the univariate effect of the diet type on glucose curves have been analyzed and then more complex fosr models with two factors (diet and patient factors) and scalar variables (nutrients) have been constructed. The most complex model including all effects of the independent variables is defined by the equation

$$g_{ij}(t) = \beta_0(t) + I_R^j \beta_R(t) + I_Q^j \beta_Q(t) + \alpha_i(t) + \sum_{k=1}^K x_k^{ij} \beta_k(t) + \varepsilon_{ij}(t),$$

where i indicates the patient ($i = 1, \dots, 9$), j indicates the day of observation ($j = 1, \dots, 28$), $g_{ij}(t)$ is the glucose curve observed the day j for patient i , I_R^j takes value 1 for regular diet and 0 for Quinoa diet, $I_Q^j = 1 - I_R^j$ is the indicator of Quinoa diet, x_k^{ij} is the content of nutrient k in the breakfast that patient i takes in the day j ($k = 1, \dots, K$) and $\varepsilon_{ij}(t)$ is a random noise function with expected value 0 for all t and independent from noise function corresponding to other days or patients. According to this model, the overall shape of glucose curves is described by the functional coefficient $\beta_0(t)$, the diet effect is summarized by the functions $\beta_R(t)$ and $\beta_Q(t)$ (by construction, they verify that $\beta_R(t) = -\beta_Q(t)$), functions $\alpha_i(t)$ measure the individual effects (by construction, $\sum_{i=1}^9 \alpha_i(t) = 0$) and $\beta_k(t)$ function shows the effect of every nutrient k . The functional

regression models have been fitted by penalized flexible functional regression, as implemented in the function pffr of the R package refund.

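### The study is called a cross-over, but all nine participants take regular diet then quinoa diet, so a common second-period step cannot be separated from diet in the clinic outcomes or the glucose curves

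*Combined protocol and SAP*

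**What the plan says.** The Study protocol section opens with "This study was a pilot clinical trial according to a cross-over design", and the Study design section repeats it: "The study was a cross-over pilot clinical study consisting of two periods". The first period is observation on the usual diet and the second is the quinoa intervention. The same section explains the order: "for this reason all participants initiated this period and wash-out term was no needed". The Study food section adds that each person's quinoa supply was matched to what their RD dietary record showed, so QD could only come second. No reverse sequence, randomised order or concurrent control is described.

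Blood samples and anthropometrics are taken once per diet, at V3 (day 28) and V5 (day 56). Under Calculations and Statistical Analyses they are compared by the Wilcoxon signed rank test. Glucose sensors are worn for the first 14 days of RD and from V3 to V4 (day 42). The breakfast glucose curves are modelled on diet, patient and nutrient content. That section presents the RD-QD term as the effect of diet, and the document title speaks of beneficial effects "in the Prevention of Type 2 Diabetes Mellitus".

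**The concern.** A cross-over separates treatment from period because different participants take the treatments in different orders. With a single order, every QD observation is also a second-period observation. The plan's own notation shows this: the diet indicator carries the day index j but not the patient index i, so diet depends on day alone.

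The plan uses the fixed order only to explain why no wash-out was needed. Wash-out deals with carry-over, and its absence is not a fault here because the first period is the usual diet. A change that affects everyone between the two periods is a different problem, and the document does not mention it. A reader who trusts the cross-over label, the diet wording and the title would credit quinoa with any RD-QD difference, although the design delivers only a difference between periods.

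**Working it through.** The plan gives no figure for this, so the check is whether diet and time can be told apart in the planned layouts.

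**Inputs from the document.** Nine participants; clinic visits on days 28 and 56; sensor windows of about days 1-14 (RD) and 29-42 (QD). The model's 28 observation days agree with 14 + 14. Let Q = 1 on quinoa days and 0 otherwise.

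**Clinic outcomes (9 people x 2 visits = 18 rows).**
- Nine patient levels plus one diet contrast: rank 10.
- A second-period step equals Q exactly, so the rank stays 10.
- A linear day term takes the values 28 and 56, which is 28 + 28Q, so the rank again stays 10.
- Any other common time effect also has just two values here, so it is confounded in the same way.

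**Glucose curves (9 x 28 = 252 rows, at each time point of the curve).**

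| Terms | Rank | Rank with period step |
|---|---|---|
| Diet only | 2 | 2 |
| Diet + patient | 10 | 10 |
| Diet + patient + 4 simulated nutrients | 14 | 14 |
| Diet + patient, two sequences (5 RD-QD, 4 QD-RD), for comparison | 10 | 11 |

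The diet + patient row is a reading of the section's general description of its more complex models. The nutrient row assumes nutrients that are not collinear. A step of 5 units with no diet effect comes back as a diet estimate of 5.0.

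**Linear drift in the glucose curves.** The window midpoints are (1 + 14)/2 = 7.5 and (29 + 42)/2 = 35.5. A drift of b per day therefore shifts the diet-only and diet + patient contrasts by b x (35.5 - 7.5) = 28b. Nutrient terms could absorb part of it. The document gives no value for b.

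This drift can be estimated in principle: patient + diet + day has 11 columns and rank 11. The precision is poor:
- variance of day within a window = (14² - 1)/12 = 16.25; between windows = (28/2)² = 196
- squared diet-day correlation = 196/212.25 = 0.923, so the correlation is 0.96
- variance inflation = 212.25/16.25 = 13.06, and its square root is 3.61
- SE of the diet contrast without a day term = σ√(1/126 + 1/126) = 0.126σ, where 126 = 9 x 14
- SE with a common day term = 0.126σ x 3.61 = 0.455σ

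Here σ is the day-to-day SD. The figures assume complete windows, independent days and one common slope.

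**Illustration for the clinic outcomes.** With n = 9, the exact two-sided Wilcoxon test at a nominal 5% rejects when the smaller rank sum is at most 5. Its size is 2 x 10/512 = 0.039. With no diet effect and a common period shift of 0.25, 0.5 or 1.0 SD of the paired differences, simulation gives rejection in about 8%, 22% and 68% of studies. In a 5/4 two-sequence layout, a rank-sum test on the period differences stays near 3% at each of these shifts. The shifts, normal differences and the 5% level are assumptions; none is in the document.

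**The case against.** The strongest reply is that nothing is hidden. The sentence after the label gives the order and the reason for it, the study is called a pilot, and no randomised order is claimed. Each person is their own control. The clinic baseline is V3, after 28 days of monitoring, which should reduce familiarisation effects and regression to the mean after selection on glucose. Sensor wear and the 14-day record are the same in both periods (at V3 "a new empty 14-day dietary record was given").

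Much of this stands. The order is disclosed and has a practical reason, and the late baseline makes some period effects less likely. But pairing and patient terms remove stable differences between people, not a change shared by all nine, and disclosure of the order does not make the contrast a diet effect.

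Some stronger readings are tempting, and the document does not support them:
- A reader might infer that no time effect of any kind can be separated from diet. That holds for the clinic outcomes and for a step in the glucose curves. It is too broad for linear drift in the curves, which is estimable, though poorly.
- A reader might infer that a period effect occurred, or that the illustrated rejection rates are evidence of one. They are the ordinary power curve of the test for any shift. The document has no data on the size of a period effect.
- A reader might blame the extra product-collection contact during QD. Collection was weekly "for conservation reasons but also to ensure that they followed an adequate consumption", so it may be part of the intervention, and the exact timing is in a figure not available here.
- A reader might look to the activity questionnaire ("Participants were asked about their physical activity and exercise practice during those past 4 weeks") to settle the matter. A paired V3-V5 comparison of it is descriptive only; it cannot separate period from diet.

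**Conclusion.** The point holds. The cross-over label implies a separation of period from diet that a single sequence cannot provide, and the RD-QD contrast should not be called a diet effect. The confounding is exact for a common second-period step in both outcome sets, and for any common time change in the clinic outcomes. These results follow from the layout and need no assumed effect size. For the glucose curves, linear drift is a lesser problem: it is left out of the model, biases the contrast by 28b with b unknown, and can be adjusted for only with an SE about 3.6 times larger.

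Dietary intake is in the same Wilcoxon set, but it comes from the records collected at V2 and V4 and mainly shows whether the diet was delivered. The argument does not rest on it.

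**What to change.** The text describes a study already carried out, so the order cannot change. The remedy is in labelling and reporting:

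1. Replace the cross-over label in the Study protocol and Study design sections with *single-arm, fixed-sequence before-after pilot*.
2. Report V5 minus V3 and QD minus RD as changes between periods, and call the model term a period/diet contrast.
3. State as a limitation that no reanalysis can remove a common period step in either outcome set, or any common time change in the clinic outcomes.
4. Limit conclusions to feasibility and hypothesis generation, and bring the title's wording on benefit and prevention into line.
5. Optionally, add a common linear day term to the glucose model, using both sensor windows. Report it as an imprecise sensitivity analysis that cannot address a step.

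No new data are needed. The cost is some rewording, one optional model fit, and a weaker headline claim.

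### The breakfast-curve regression gives no interpolation step and has nothing to carry within-curve correlation, so standard errors for the diet effect would be too small if grid rows are treated as independent

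*Combined protocol and SAP*

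**What the plan says.** All references are to the combined protocol and SAP.

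- **Readings.** Under Measures, participants are trained to "obtain electronically all the glucose records concentrations every 15 minutes".
- **Window and interpolation.** Under Calculations and Statistical Analyses, the curves are interpolated linearly "in order to have observations for each patient at equal time points". The response is the breakfast segment, over an interval "that begins half an hour before the start of breakfast and ends two hours later". The curves are time-aligned by warping before modelling. Neither the step of the common grid nor the number of points is given.
- **Model.** The first model contains diet only. The fullest one has an overall curve, diet, one functional effect for each of nine patients, and nutrient effects, with 28 observation days per patient. No term is specific to a patient's curve on a given day.
- **Error.** The error term "is a random noise function with expected value 0 for all t and independent from noise function corresponding to other days or patients".
- **Fit.** The "regression models have been fitted by penalized flexible functional regression", using pffr in the R package refund. No residual-covariance, robust-variance or resampling option is named. The text mentions no confidence band, standard error or test for the diet effect.

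**The concern.** An interpolated value is a weighted average of the two readings on either side of it, so interpolation adds rows to the data set but no information. The real readings are also unlikely to be independent within a meal: a breakfast that runs high at 30 minutes tends to run high at 45. The written model recognises this implicitly, because its error is a whole function for each patient and day. For standard errors to reflect that, the fit needs something that represents the error function: a curve-level random function, a residual covariance, or resampling of whole curves or participants. None is stated.

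If the fit counts each grid row as a separate observation, the standard errors of the diet curve are too small, and they shrink further as the grid is made finer although the data are unchanged. This regression is the plan's analysis of how diet affects monitored glucose. A statement that quinoa changes glucose over part of the breakfast window could then rest partly on the chosen grid step.

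**Working it through.** The plan gives no band width, power or alpha for this model, so there is no figure of its own to reproduce.

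**Inputs from the documents.** Reading interval 15 min (Measures). Window −30 to 120 min, nine patients, 28 days each (Calculations and Statistical Analyses).

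**Counts**

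- Readings per curve: 150/15 + 1 = 11 (10 if the readings are out of phase with the window).
- Curves: at most 9 × 28 = 252.
- Real readings: 252 × 11 = 2,772.
- Model rows: 2,772 on a 15-min grid (11 points), 4,032 at 10 min (16 points), 7,812 at 5 min (31 points), 38,052 at 1 min (151 points).

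**Standard-error ratio.** Let B be a cubic B-spline basis evaluated on the grid, G = (B′B)⁻¹, and C the correlation matrix of the 11 readings. Let W be the linear-interpolation matrix, S = WCW′ the covariance of a curve on the grid, and s² the mean of the diagonal of S. At each time point,

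true SE / independence SE = √[ diag(B G B′S B G B′) / diag(s² B G B′) ].

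**Assumptions, because the documents give none of these.** Correlation exp(−lag/range) with range 15, 30, 60 or 120 min, that is 0.37 to 0.88 between adjacent readings; 5 or 8 spline functions; no smoothing penalty; no alignment step; grid rows treated as independent in the fit. Different curves are taken as independent, as the plan states.

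Median ratio over the window:

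| Grid | 5 functions, range 30 / 60 / 120 | 8 functions, range 30 / 60 / 120 | Range 15 (8 and 5 functions) |
|---|---|---|---|
| 15 min | 1.44 / 1.53 / 1.58 | 1.17 / 1.19 / 1.20 | 1.12 and 1.28 |
| 10 min | 1.82 / 1.90 / 1.94 | 1.47 / 1.48 / 1.48 | 1.44 and 1.67 |
| 5 min | 2.53 / 2.64 / 2.69 | 2.06 / 2.08 / 2.09 | 2.01 and 2.32 |
| 1 min | 5.54 / 5.76 / 5.86 | 4.63 / 4.66 / 4.68 | 4.54 and 5.13 |

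Averaging over 0 to 120 min instead of taking the median raises the upper ends to 1.62, 1.98, 2.75 and 6.04. At single time points the ratio varies: near the ends of the window it falls to about 1.0 on the 15-min grid, and in the middle it is higher than the median.

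**Where the factor comes from.** If the 11 readings were truly independent, the ratio would be 1.00 at 15 min, 1.85–1.94 at 5 min and 4.24–4.43 at 1 min. Most of the growth with a finer grid is therefore the added rows. The excess on the 15-min grid is real correlation between readings.

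**Coverage.** A nominal 95% pointwise band covers 2Φ(1.96/ratio) − 1:

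- ratio 1.1 to 1.6: 93% to 78%;
- ratio 2 to 2.8: 67% to 52%;
- ratio 4.5 to 6: 34% to 26%.

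**Limiting case.** If the diet effect is smoothed to near-constant, the ratio is √(1 + (m − 1)ρ) for m points with average correlation ρ. For ρ from 0.3 to 0.9:

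- m = 11: √4.0 to √10.0 = 2.0 to 3.2;
- m = 31: √10 to √28 = 3.2 to 5.3;
- m = 151: √46 to √136 = 6.8 to 11.7.

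**The case against.** A reader might infer that the plan counts 11 readings as dozens of observations and that its diet-effect bands are several times too narrow. The documents do not support that as a statement of fact, for four reasons.

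- The grid step is not given. The stated aim of common time points is met by a 15-minute grid, which adds no rows. Dozens of points per curve needs a step of about 5 minutes or less.
- The written model does not assume independence within a curve. Its independence clause concerns other days and other patients only.
- That pffr was run with independent residuals is an assumption. The text names the function and package, not the settings.
- No band or test is mentioned, so there is no reported width to be wrong.

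All four points stand. They limit the size that can be claimed, but the gap remains: the model as written needs a way to carry within-curve correlation into its standard errors, and none is stated. The median ratio also exceeds 1 on a 15-minute grid with no added rows.

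It can also be said that the calculation uses an unpenalized spline without alignment, whereas the plan aligns the curves and penalizes the fit. The figures are therefore illustrative. Penalization does not remove the problem, because stronger smoothing moves the ratio towards the larger near-constant case. The effect of alignment was not examined. Finally, this is a nine-person pilot with no stated alpha for this model, which lowers the stakes without making a wrong standard error useful.

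**Conclusion.** The point holds in conditional form. Each curve has about 11 real readings on a grid of unstated step, and the specified fit has no curve-level term, residual covariance or resampling. If rows are treated as independent, the standard errors for the diet effect are too small by roughly 1.1–1.6 times at 15 minutes, 2–2.8 at 5 minutes and 4.5–6 at 1 minute, and by more under heavy smoothing or a near-constant effect. The direction is robust over the typical part of the window in every correlated scenario tried. The size depends on the assumed grid, correlation and basis, and on the residual settings actually used. These figures concern within-curve correlation only; they do not include variation between participants in the response to diet. The gap should be closed before any band or p-value for diet is reported.

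**What to change.** 1. State the interpolation step, the number of grid points after alignment, the spline basis and the residual settings used in pffr.
2. Keep the pffr fit, including nutrients, for the estimated curves.
3. Take any band or p-value for diet from a method whose unit is the participant. Either option serves:
   - a bootstrap that resamples whole participants around the fitted model, with each drawn participant given a separate patient label;
   - nine mean difference curves (quinoa minus regular diet), all 2⁹ = 512 sign flips, and the maximum over time for a simultaneous band and one global p-value.
4. If model-based standard errors are kept, add a curve-level functional random effect or a residual covariance, use a grid no finer than the 15-minute readings, and check the result against step 3.

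**Costs to state.** The work is a modest amount of code and no new data. Bands will be wider. The sign-flip test has a smallest two-sided p of 2/512 = 0.0039 and makes no nutrient adjustment. It also rests on the differences being symmetric under the null hypothesis, because all participants took the regular diet first and order was not randomised. A bootstrap keeps the nutrient terms, but with nine participants it is itself slightly optimistic: for a simple mean its standard error is too small by √(8/9) = 0.94.

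### The first diet analysis of the breakfast glucose curves leaves out the patient, so its standard errors are miscalibrated and its estimate is exposed to curve loss that differs between people and diets

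*Combined protocol and SAP*

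**What the plan says.** Under Participants: "Nine subjects were included". Under Study design, all of them follow RD first and then QD. A sensor is worn for two weeks in each period. For RD: "After the first 14 days of this, a second visit (V2) was made", when that sensor was collected. For QD, a new sensor is placed on day 28, and "On the next visit the day 42 (V4) the Freestyle Libre® sensor was collected".

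Under Calculations and Statistical Analyses, the model sequence for the breakfast curves begins: "Firstly, the univariate effect of the diet type on glucose curves have been analyzed". It goes on: "then more complex fosr models with two factors (diet and patient factors) and scalar variables (nutrients) have been constructed". The equation for the largest model contains functions αi(t), which "measure the individual effects", and errors taken as independent across days and patients. In that equation "j indicates the day of observation", running from 1 to 28.

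The same section compares anthropometric, blood and dietary variables with a paired test, the Wilcoxon signed rank test. It does not say which functional model carries the diet conclusion, whether the diet-only fit is only descriptive, whether bands or tests are taken from it, or how missing curves are handled.

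**The concern.** Each participant is his or her own control, which is the main strength of a nine-person study. A diet-only model discards this, with two consequences. Stable differences between people go into the residual, so the standard error no longer describes the uncertainty of a within-person difference. And the RD and QD means can be taken over different mixes of people if some lose more curves on one diet than on the other.

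The later diet-plus-patient models are described together with nutrients. The text does not clearly list a diet-plus-patient model without nutrients. The diet-only fit may therefore be the only listed estimate of the overall diet effect that is not adjusted for what was eaten at breakfast. A reader who wants that effect might have to take it from the one model that ignores pairing.

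**Working it through.** The plan gives no SD, effect size or standard error, so there is no figure of its own to reproduce. All SDs below are assumptions in mg/dL, and a single time point stands in for the whole curve.

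**Inputs.** Patients: 9 (Participants). Sensor days: 14 on RD and 14 on QD (Study design). 14 + 14 = 28 agrees with the day index in the model. If complete, there are 9 × 14 = 126 curves per diet and 252 in all. Write sb for the between-person SD, sw for the day-to-day SD and sd for the SD of people's own diet responses.

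**1. Standard error, complete data, equal responses (sd = 0).** The point estimate is the same with or without the patient term.
- With patient: SE = √(2·sw²/126).
- Diet only: SE = √(2·(0.896·sb² + sw²)/126), where 0.896 = 28 × 8/250 is the share of between-person variance left in the residual.
- At sb = sw = 12: √(2 × 144/126) = 1.51 with patient, and √(2 × 273.0/126) = 2.08 diet only. The ratio is 1.38.
- In general the ratio is √(1 + 0.896·sb²/sw²): 1.18 at sb/sw = 10/15 and 1.55 at 15/12. Simulation gave 1.18, 1.37 and 1.53 for the three settings.

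**2. Standard error when responses differ.** The true SE is √(2·sw²/126 + sd²/9). At sb = sw = 10 and sd = 5 this is √(1.587 + 2.778) = 2.09. Simulation with complete data, 3,000 runs per row, nominal level 5%:

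| sb, sw, sd | True SE | Diet only: mean SE, type I error | Diet + patient: mean SE, type I error |
|---|---|---|---|
| 10, 10, 0 | 1.26 | 1.72, 1.2% | 1.26, 5.3% |
| 15, 10, 0 | 1.26 | 2.15, 0.2% | 1.26, 4.8% |
| 10, 10, 5 | 2.09 | 1.78, 10.2% | 1.30, 21.9% |
| 15, 10, 5 | 2.04 | 2.19, 5.1% | 1.29, 21.1% |

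The diet-only SE passes from too large to too small roughly where sd²/9 = 2 × 0.896·sb²/126, that is at sd ≈ 0.36·sb. For sb = 12 this is about 4.3 mg/dL, ignoring the small part of the response variation that also enters the diet-only residual.

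**3. Shift from lost curves.** The diet-only estimate moves by Σ(n_iQ/n_Q − n_iR/n_R)·αi, where n_iQ and n_iR are person i's curves on each diet and n_Q and n_R are the totals. Take one person 24 above the other eight, with full RD data (share 14/126 = 1/9).
- No QD curves: 0 − 24/9 = −2.67.
- 5 of 14 QD curves, so n_Q = 8 × 14 + 5 = 117: 5 × 24/117 − 24/9 = 1.03 − 2.67 = −1.64.
- For a person only 10 above the others who loses 7 of 14 QD curves: 10 × (7/119 − 1/9) = −0.52.
- All nine lose 4 QD curves each: 0. One person loses 7 in both periods: 0.

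With the patient term, the shift due to patient levels was 0 in every pattern tried.

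**The case against.** The sentence that introduces the diet-only fit goes on to models that contain the patient. The text on the full model also reads the diet effect from βR(t) and βQ(t) in an equation that includes αi(t). An unadjusted fit followed by adjusted ones is a common descriptive sequence. This stands, and it confines the fault to the first fit. It does not remove the fault, because the plan neither labels that fit descriptive nor clearly lists a nutrient-free model with the patient.

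No band, p-value or test is stated for the diet-only fit. That is also true: a standard error is a presumed output, and the point matters only if inference is drawn from the fit.

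With complete data and equal responses the fit is merely conservative, with the same point estimate. This stands for that case only.

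The loss examples are severe: a person two between-person SDs high (24 against 12) who loses 9 or all 14 QD curves. The documents report no such loss. They do make some loss plausible, since readings depend on a scan at least every eight hours and each curve depends on a marked breakfast start.

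Finally, adding a fixed patient term can worsen inference. In the third row of the table it raises type I error from 10.2% to 21.9%. This is correct, and the remedy has to allow for it.

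**Conclusion.** The point holds for the first listed diet model, and for that model only. Its standard errors are miscalibrated. They are about 1.2 to 1.5 times too large with complete data and similar responses, at assumed SDs of 10-15 between people and 12-15 day to day. They can be too small once responses differ enough between people. Its estimate also moves when the pattern of loss across people differs between diets, by −1.6 to −2.7 mg/dL in the two examples with a person 24 above the other eight.

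Some stronger readings are tempting but are not supported:
- A reader might infer that the glucose analysis as a whole ignores pairing. The later models include the patient.
- A reader might infer that any unequal loss biases the estimate. Equal proportional loss in everyone, or the same loss in both periods for a person, shifts nothing.
- A reader might infer that the bands are always too wide. That requires people to respond much alike.
- A reader might infer that the diet-only result is the one to be presented. The documents do not say so.
- A reader might infer that the existing patient term is a full cure. It removes the shift, but with independent errors it can give bands that are too narrow.

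The sizes rest on assumed SDs and a single time point. The direction of the shift depends on who loses curves.

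**What to change.** Replace the diet-only fit with a diet + patient model without nutrients as the basis for the overall diet effect, and keep the diet-only mean curves as a descriptive plot with no band or test. Take the error bars from a version in which the diet response varies by patient: either a patient-by-diet random functional effect, or an analysis of the nine per-person differences in mean curve. Report the number of usable breakfast curves per participant and diet, so that a reader can see whether loss was uneven.

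The patient factor is already coded and no new data are needed. The cost is slightly more analysis work, and possibly wider bands than the fixed-patient model gives.
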